6.6.3 Retention of Data

At study close-out, the CDM will archive all the final datasets, CRFs, design documentation, protocol and all other documents in a study data repository. Records may not be destroyed without written permission from NIAID/DMID.

Study sites will maintain study records and reports, including, but not limited to, CRFs, source documents, ICFs, test results, and medication inventory records for 3 years after study completion. The investigators may transfer custody of the records to another person who will accept responsibility for them. Notice of transfer must be given to the sponsor preferably before, but no more than ten days after, the transfer.

No records will be destroyed without the written consent of the sponsor. It is the responsibility of the sponsor to inform the investigators and FHI 360 CDM when these documents no longer need to be retained.

6.6.4 Protocol Deviations

A protocol deviation (PD) is any noncompliance with the study protocol, GCP or protocol-specific Manual of Procedures requirements. The noncompliance may be either on the part of the participant, the SI, or other study personnel. As a result of deviations, corrective actions will be developed through a plan agreed upon by the site, the study Principal Investigator and DMID and then implemented promptly.

It is the responsibility of the SI and other study personnel to use continuous vigilance to identify and report deviations within five working days of identification of the PD, or within five working days of the scheduled protocol-required activity. All deviations must be promptly reported to DMID using the approved DMID PD form and reporting methods.

All deviations from the protocol must be addressed in study participant source documents. A completed copy of the DMID PD form must be maintained in the Regulatory File. PDs must be sent to the local IRB/Independent Ethics Committee per their guidelines. The SIs and other study personnel are responsible for knowing and adhering to their IRB requirements.

7 SAFETY ASSESSMENT AND REPORTING

This clinical study poses only minimal risk to study subjects. Minimal risk is defined by 45 US CFR 46.102 (j) as follows:

“Minimal risk means that the probability and magnitude of harm or discomfort anticipated in the research are not greater in and of themselves than those ordinarily encountered in daily life or during the performance of routine physical or psychological examinations or tests.”

Our experience indicates there will be infrequent problems with AEs. The PRE-PEN® (benzylpenicilloyl polylysine injection USP) kit was FDA approved in 2009 for the assessment of sensitization to PCN (benzylpenicillin or penicillin G) in those patients suspected of having a clinical hypersensitivity to PCN. Rarely, a systemic allergic reaction including anaphylaxis may follow a skin test with PRE-PEN®. To decrease the risk of a systemic allergic reaction, we will perform prick (puncture) skin testing first. Intradermal skin testing will be performed only if the prick test is entirely negative. Occasionally, patients may develop an intense local inflammatory response at the skin test site. Rarely, patients will develop a systemic allergic reaction, manifested by generalized erythema, pruritus, angioedema, urticaria, dyspnea, hypotension, or anaphylaxis. We will use standard of care treatment for any reactions. Study staff will be trained and anaphylaxis kits will be available at all sites. If necessary, subjects will be referred to local urgent care or emergency department facilities.

7.1 Safety Assessments

For the purposes of safety assessment and reporting, there are three potential safety checkpoints in this clinical trial:

- 1) Pre-skin testing
- 2) Post-skin testing
- 3) Oral challenge

These checkpoints are applicable to all subjects consented and enrolled after the initial screening questions.

7.1.1 Pre-Skin Testing

Prior to skin testing, study staff will verify that subjects:

- Have not responded ‘yes’ to any of the high-risk PCN allergy history questions on the PCN (B-lactam) Allergy History Screening Questionnaire
- Have not used oral antihistamines within the past week
- Do not have severe eczema, psoriasis, or other major skin conditions in the areas where testing will be done (usually the arms)

- Do not have large tattoos on their arms
- If HIV positive, are on HAART
- If HIV positive, CD4 not <200 in the past 6 months

7.1.2 Post-Skin Testing

- Subjects will be observed for 30 + 5 minutes and 60 + 5 minutes after skin testing. Assessment of elicited reactivity to PCN will include local skin reactions including erythema, induration and itching which will be evaluated both by self-report and physical exam. Systemic reactions are extremely rare.
- Subjects with positive skin tests will not progress to oral challenge step.

An impending generalized reaction to immediate hypersensitivity skin testing is unusual. If any acute reactions occur, they will be treated as necessary and reported to the IRB and DMID as required.

7.1.3 Oral Challenge

Pregnancy status will be verified. Pregnant women will not be enrolled in the DOC group.

Prior to the oral challenge, vital signs will be recorded (heart rate, respiratory rate, blood pressure and peak flow). A focused PE will be performed (eyes, pharynx, lungs and skin). Subjects will be observed for 60 minutes \pm 10 minutes after the amoxicillin is administered. Vital signs, peak flow measurement and focused PE will be repeated after the 60-minute observation period \pm 10 minutes.

After oral challenge, subjects will be assessed for the most common elicited reactions associated with amoxicillin which will be graded and documented using the Toxicity Table (Appendix C):

- Cardiovascular: lightheadedness, loss of consciousness
- Skin: urticaria, flushing, rash, angioedema
- HEENT: conjunctivitis, rhinitis, congestion
- Respiratory: shortness of breath, wheezing
- GI: nausea, vomiting, diarrhea

Data will be collected on reactions to amoxicillin as a diagnostic tool for defining an allergic reaction that was not identified by the skin testing. Unanticipated reactions that place the subject at increased risk will be recorded on the AE CRF and reported to the IRB and DMID according to their reporting guidelines.

Subjects will be provided with contact information for study staff to report the development of additional symptoms.

7.2 Reporting

Federal regulations require that institutions engaging in human subjects' research have written procedures to ensure investigators properly report certain events to the IRB. Events must be reported promptly after the event is discovered or within 10 working days after discovery of the event.

All potential unanticipated problems involving risks to subjects or others (UPIRSO) must be reported. An event is considered an UPIRSO when it meets all of the following criteria:

1. It is unexpected (in terms of nature, severity, or frequency) given (a) the research procedures that are described in the IRB-approved research protocol and informed consent document; and (b) the characteristics of the population being studied;
2. It is related or possibly related to participation in the research (i.e. there is a reasonable possibility that the incident, experience, or outcome may have been caused by the procedures involved in the research);
and
3. It places subjects or others [e.g., study staff or relatives of a subject] at a greater risk of harm (including physical, psychological, economic, or social harm) than was previously known or recognized.

Other events that require prompt reporting include potential breaches of confidentiality and unresolved participant complaints.

8 STATISTICAL CONSIDERATIONS

8.1 Study Outcome Measures

8.1.1 Primary Outcome Measures

The following primary outcome measures will be used to address the primary study objectives:

- Algorithm / PCN (B-lactam) allergy history screening questionnaire performance in ambulatory STD populations, specifically the NPV of the algorithm on true PCN (B-lactam) allergy.
- In ambulatory STD patients who report a history of PCN (B lactam) allergy and who have low-risk histories, determine the prevalence of PCN reactivity validated either by skin test or by direct oral challenge.

8.1.2 Secondary Outcome Measures

The following secondary outcome measures will be used to address the secondary study objectives:

- Acceptability
 - Proportion of study subjects who find the testing procedures to be helpful.
 - Reasons why study subjects refuse to participate in the study or find the testing procedures to be of no value.
 - Proportion of study subjects who were negative on oral challenge who now feel confident in taking PCN or similar antibiotics.
 - Proportion of study providers who will not offer PCN allergy assessment in the future.
- Feasibility
 - Proportion of study providers who will offer PCN allergy assessment in the future.
 - Reasons why study providers will not offer PCN allergy assessment in the future.
- Both acceptability and feasibility
 - Types and frequencies of elicited reactivity to PCN through skin testing and oral challenge among study subjects.

8.2 Sample Size Considerations

The sample size for this study was selected to have adequate study power to conclude a high NPV of the PCN (B-lactam) allergy history screening questionnaire in ruling out the presence of true PCN (B-lactam) allergy. To address the objective properly, we applied Steinberg's et al.³² approach to obtain the minimal sample size needed to achieve a lower 95% confidence bound for NPV that exceeds the NPV with a useless test at a fixed level of significance with a given study power. Based on this approach, the sample size calculation depends on the prevalence of PCN allergy in the population and among observed study participants and the sensitivity and specificity of the PCN allergy diagnostic kit (PRE-PEN®). To target at least 85% power at 5% of significant level, the listed sample sizes (see table) provide lower 95% confidence bounds for NPV under the following various assumptions:

- The true population prevalence with PCN allergy: 1%, 3%, 5%
- The observed % of PCN allergy in this study: 1%, 3%, 5%
- The PCN allergy diagnostic kit with sensitivity at least 85% and specificity 95%
- 5% of participants who report a PCN allergy history will have a high-risk allergy history and therefore will not proceed to skin testing.

Population prevalence of PCN allergy	Observed % of PCN allergy in study	Estimated NPV	The lower 95% confidence bound for NPV						
			99.0%	98.4%	97.9%	97.5%	97.3%	97.0%	95.0%
1%	1%	99.84%	1259	796	635	556	526	488	351
	3%	99.51%	420	265	212	185	175	163	117
	5%	99.18%	252	159	127	111	105	98	70
3%	1%	99.84%	8119	2964	1958	1559	1421	1259	759
	3%	99.51%	2707	988	653	520	474	420	253
	5%	99.18%	1624	593	392	312	284	252	152
5%	1%	99.84%	113000	9519	4770	3378	2950	2483	1259
	3%	99.51%	37547	3174	1590	1126	984	828	420

	5%	99.18%	22533	1905	954	676	590	497	252
--	----	--------	-------	------	-----	-----	-----	-----	-----

For example, with 3% PCN allergy prevalence in population and among observed study participants, the NPV for a useless test is 97%. A useful PCN (B-lactam) allergy history screening questionnaire should have the lower 95% confidence bound for NPV greater than 97%. Based on the list a minimum sample size of 988 subjects who reported to have PCN allergy history would provide an estimated NPV = 99.51% with 85% power to conclude that the NPV of the study allergy history screening questionnaire is least 98.4% at 5% significant level.

8.3 Participant Enrollment and Follow-Up

The final statistical report will include an accounting of all subjects screened, including the number enrolled, the number excluded, the number with high-risk history of PCN allergy, the number who refused to participate in skin testing, the number who received skin testing, the number excluded from oral challenge, the number who refused oral challenge, the number who received oral challenge and other key study status indicators. The reason for excluding any study subject during the study process will be documented. The study population flow chart will be provided.

8.4 Analysis Plan

A detailed statistical analysis plan (SAP) will be developed prior to performing any analyses. The following is a summary of the planned analyses. Any changes made to this summary plan will be documented in the detailed SAP.

8.4.1 Primary analysis

The primary analysis will estimate with corresponding exact 95% confidence intervals:

- The prevalence of PCN reactivity validated either by skin test or by direct oral challenge among those participants who report a history of PCN (B-lactam) allergy and who have low-risk histories.
- The NPV on true PCN (B-lactam) allergy of the algorithm / PCN (B-lactam) allergy history screening questionnaire performance in the study population.

The NPV for each question will be estimated and its performance will be assessed.

To construct a short standardized post-study questionnaire (4-6 questions) from the PCN (B-lactam) allergy history screening questionnaire, we will use Item Response Theory (IRT) to evaluate each question item's discrimination ability of true PCN (B-lactam) allergy and use variable importance evaluation functions to indicate which questions are most useful for

predicting the true PCN (B-lactam) allergy. Based on the results of IRT and variable importance analyses, we will then apply machine learning approaches (e.g., random forest approach via R packages of caret)³³ to select a short post-study questionnaire that has the highest NPV among those possible short questionnaires with 4-6 selected questions.

8.4.2 Analysis of Secondary Endpoints

The frequency and the percentage of participants 1) who experienced elicited reactivity to PCN allergy skin testing in the PST Group and oral challenge in both groups; 2) who refused to participate the study; 3) who found the testing procedures of no value will be tabulated by study site. The proportions of participants 1) experiencing elicited reactivity to penicillin allergy testing; 2) reporting reasons for refusing to participate in the study or finding the testing procedures to be of no value; 3) describing confidence in taking PCN or similar antibiotics among those who were negative on oral challenge will be calculated with corresponding exact 95% confidence intervals.

The same approach will also be used to evaluate the feasibility of providers who will offer the PCN allergy assessment in the future and the reasons among those providers who will not offer the PCN allergy assessment in the future. The evaluation of the secondary endpoints will be conducted by intervention group and overall

9 SUBJECT CONFIDENTIALITY

The participating investigators, their staff, and the sponsor(s) and their agents hold participant confidentiality strictly in trust. This confidentiality includes clinical information relating to enrolled participants. All clinical information will be maintained at the sites.

The study protocol, documentation, data, and all other information generated during participation in the study will be held in strict confidence. No information concerning the study, or the data generated from the study, will be released to any unauthorized third party without prior written approval of the sponsor. Subject confidentiality will be maintained when study results are published or discussed at conferences. Authorized representatives of the sponsor or governmental regulatory agencies may inspect all documents and records required to be maintained by the investigator. The clinical study site will permit access to such records.

All records will be kept locked, and all computer entry and networking programs will be carried out with coded numbers only and with password protected systems. All evaluation forms, reports, and other records that leave the site will be identified only by a coded number.

This research is covered by a Certificate of Confidentiality from the NIH. The researchers with this Certificate may not disclose or use information, documents, or biospecimens that may identify a subject in any federal, state, or local civil, criminal, administrative, legislative, or other action, suit, or proceeding, or be used as evidence, for example, if there is a court subpoena, unless a subject has consented for this use. Information, documents, or biospecimens protected by this Certificate cannot be disclosed to anyone else who is not connected with the research except, if there is a federal, state, or local law that requires disclosure (such as to report child abuse or communicable diseases but not for federal, state, or local civil, criminal, administrative, legislative, or other proceedings); if a subject has consented to the disclosure, including for their medical treatment; or if it is used for other scientific research, as allowed by federal regulations protecting research subjects.

10 INFORMED CONSENT PROCESS

Federal regulations specify the elements of informed consent that must be conveyed to research participants through the informed consent process (see 21 CFR 50.20). It is the responsibility of the SI and his/her assigned staff to ensure that all required information has been provided to potential research participants. The consent forms for this study will be IRB approved.

Informed consent is a process that is initiated prior to the individual's agreeing to participate in the study and continuing throughout the individual's study participation. Participants may withdraw consent at any time during the trial. Study staff will provide the potential participant consent forms (as approved by the IRB) which describe the study procedures and risks in detail. Documentation of obtaining informed consent will be noted. Staff will ask the potential participant to read and review the document, or have it read to them, and will also be available to answer any questions the participant may have. Those who administer consent will provide extensive discussion of risks and possible benefits to the potential participants. Informed consent can be obtained orally, written and electronically using procedures approved by the IRB. The potential participant will provide consent before any procedures are performed specifically for the study. The potential participants will have the opportunity to discuss the study prior to agreeing to participate. A copy (or electronically) of the applicable consent form will be provided to the participant. The consent will state that the administration and quality of their medical care will not be adversely affected if they decline to participate in this study.

The study staff's approach to study subjects will be compliant with HIPAA regulations.

APPENDIX A: SCHEDULE OF EVENTS

Procedures	Enrollment Visit	Additional Visit (within 6 weeks as necessary to complete study procedures)
Written, oral, or electronic informed consent	X	
Assessment of eligibility criteria	X	
Review demographic information	X	
Administration of PCN (B-lactam) Allergy History Screening Questionnaire	X	
Review of concomitant medications	X	(X)
Allergy Validation Method 1: PST Group		
Assessment of PCN Skin Test qualification criteria	X	(X)
If additional criteria met, PCN Skin Test (prick and/or intradermal)	X	(X)
Photo documentation of skin testing (iPad)	X	(X)
Assessment of Oral Challenge qualification criteria	X	(X)
Assessment of vital signs (plus peak flow) and focused PE before and after Oral Challenge	X	(X)
If additional criteria met, Oral Challenge of 250 mg amoxicillin	X	(X)
Allergy Validation Method 2: DOC Group		
Assessment of Oral Challenge qualification criteria	X	(X)
Assessment of vital signs (plus peak flow) and focused PE before and after Oral Challenge	X	(X)
If additional criteria met, two-step Oral Challenge – initial dose of 25 mg amoxicillin followed by full dose of 250 mg	X	(X)
Completion of CRFs	X	(X)
Assessment of Adverse Events	X	(X)
Administration of subject acceptability survey	X	(X)
Provide written documentation of PCN allergy testing results or referral to allergist	X	(X)

At enrollment, all procedures will be completed unless participant cannot stay for skin testing and/or oral challenge.

(X) indicates procedures that may not have been completed during Enrollment Visit because of time constraints

APPENDIX B: PCN (B-LACTAM) ALLERGY HISTORY SCREENING QUESTIONNAIRE

Section 1: Allergy History

- 1) How long ago was the reaction to the antibiotic?
 - a. < 6 months
 - b. 6 months-1 year
 - c. 2-5 years
 - d. 6-10 years
 - e. > 10 years
 - f. Don't remember / Unknown

- 2) What was the name of the drug you reacted to?
 - a. (Please list) _____
 - b. Don't remember / Unknown

- 3) How was the antibiotic administered?
 - a. Pill or Liquid by mouth
 - b. Injection (a shot) into a muscle or through a vein
 - c. Don't remember / Unknown

- 4) When did your allergic reaction to the antibiotic start?
 - a. Less than 1 hour after the first dose
 - b. Between 1 and 6 hours after the first dose
 - c. More than 6 hours, but less than 24 hours after the first dose
 - d. 24 hours or more after the first dose
 - e. Unknown

- 5) How many days did you receive your antibiotic treatment?
 - a. One day only
 - b. About _____ days of treatment
 - c. Don't remember / Unknown

- 6) People experience many different kinds of symptoms during an allergic reaction to an antibiotic. What were the symptoms of your allergic reaction? (OK to select more than one)
 - a. Can't remember (check only after reading entire list)

- b. Non-specific symptom(s) (e.g., "sick" "thought I was a goner" "high as a kite" "like I had the flu")

Responses to the symptoms listed below should be graded on a 5-point scale:

Don't Recall /None / Mild / Moderate / Severe

Low-Risk Allergy History

- a. Isolated GI upset (*diarrhea, nausea, vomiting, abdominal pain*)
- b. Chills (*rigors*)
- c. Headache
- d. Fatigue
- e. Itching (*pruritus*), self-limited,
- f. Rash (*including maculopapular rash*)
- g. Hives (greater than 5 years ago)
- h. Flushing / redness
- i. Family history
- j. Patient denies allergy history but is in medical record

Higher-Risk Allergy History: Skin Testing and Oral Challenge Contraindicated

- a. Angioedema or swelling of lip, tongue, or around eyes
- b. Wheezing / chest tightness moderate or severe shortness of breath
- c. Throat tightness which affected ability to breathe
- d. Hypotension without rapid recovery
- e. Arrhythmia / irregular heartbeat or palpitations
- f. Syncope / pass out / dizzy
- g. Anaphylaxis or sudden drop in blood pressure
- h. Hives (5 years or less)

Late Effect Symptoms (higher-risk events occurred >24 hours after drug administration)

- a. Stevens-Johnson syndrome (*Loss >10% of skin*)
- b. Organ injury (*liver, kidney*)
- c. Low Platelets
- d. Drug reaction eosinophilia and systemic symptoms (*rash with eosinophilia and organ injury*)
- e. Acute generalized exanthem (*rash with pustules*)
- f. Dystonia or muscles became very stiff or very weak
- g. Serum sickness (*rash with joint pain, fever, myalgia*)
- h. Anemia

- i. Documented drug fever
- j. Erythema multiforme (*rash with target lesions*)
- k. Hives (5 years or less)

7) What treatment did you receive for the allergic reaction on the day it started? (OK to select more than one)

- a. No treatment
- b. Went to the hospital emergency room or urgent care center
- c. Was admitted to the hospital
- d. Given epinephrine / adrenaline
- e. Given steroid pills or injections
- f. Given a steroid cream
- g. Given an antihistamine (anti-itch pill)
- h. Antibiotic discontinued
- i. Fluids through a vein
- j. Other (please list) _____
- k. Unknown

8) Did you stop taking the antibiotic or did you finish the course?

- a. Stopped after the reaction started
- b. Continued to take the antibiotic after the reaction
- c. Don't remember

9) Since you had the antibiotic reaction, have you ever taken any of the following antibiotics?

- a. Amoxicillin/Clavulanate (Augmentin)
- b. Cephalexin (Keflex)
- c. Ceftriaxone (Rocephin)
- d. Benzathine Penicillin (Bicillin) (injections)
- e. Cefuroxime (Ceftin)
- f. Cefadroxil (Duricef)
- g. Ampicillin
- h. Amoxicillin
- i. Cefaclor (Ceclor)
- j. Cefixime (Suprax)
- k. Any other drug whose name ended with "cillin"
- l. Any other drug whose name started with "cef"
- m. Other (Please list) _____
- n. Don't know or remember

10) Since you had the antibiotic reaction, have you ever been treated for gonorrhea, syphilis or strep throat?

- a. Yes (please list medication) _____
- b. No

Section 2: Skin Testing History

Questions to ask before skin testing is performed

- 11) Have you ever been skin tested for allergy to penicillin?
 - a. Yes (if Yes, go to Q12; otherwise skip to Q13)
 - b. No
 - c. Unknown

- 12) What were the results of the skin test?
 - a. Positive
 - b. Negative
 - c. Unknown

- 13) In the past week have you taken any of the following medications, including over the counter (OTC)? (***Include only medications that you have taken orally, no skin or eye medications***)
 - a. OTC cough and cold remedies containing antihistamines
 - b. Benadryl
 - c. Non-sedating antihistamines (Zyrtec, Allegra, Claritin, Xyzal)
 - d. Antivert / meclizine, Dramamine and Phenergan
 - e. Hydroxyzine (Atarax/Vistaril)
 - f. Other (please list) _____
 - g. None – I have not taken any of these medications

(If Yes to a, b, c, d or e, exclude from skin test)

Section 3: Subject Acceptability Survey**Questions to ask after skin testing and oral challenge procedures are completed**

FOR ALL SUBJECTS

14) Did you find the penicillin testing procedures to be helpful?

(Scale of 1-5, where 1 is extremely helpful, 5 is not helpful at all)

(if 4 or 5, go to Q15; otherwise skip to Q16)

15) Why were the penicillin testing procedures not helpful?

- a. Took too long
- b. Testing was uncomfortable
- c. Other (Please list) _____

16) Were you comfortable with allergy testing conducted in settings where STD services are provided rather than by an allergist?

(Scale of 1-5, where 1 is extremely comfortable, 5 is not comfortable at all)

17) If a friend or family member had a history of penicillin allergy, would you refer them for testing?

(Scale of 1-5 where 1 is definitely yes, 5 is definitely no)

FOR SUBJECTS WHO HAVE BEEN SKIN TESTED AND ARE NEGATIVE FOR PCN ALLERGY

18) How confident are you that you can now take penicillin or similar antibiotics?

(Scale of 1-5 where 1 is very confident and 5 is not confident at all)

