2.2.4 Cephalosporin Challenge in Surgical Patients

One of the unique aspects about the STD setting is that antibiotic therapy is either single dose or very short term. This is especially true with gonorrhea, which is treated with a single dose of ceftriaxone. An analogous situation is perioperative antibiotic prophylaxis, in which cefazolin is almost universally recommended as first line therapy. Because of data demonstrating that surgical site infection is higher in patients treated with non-B-lactam regimens,⁹ there has been interest in this area. Vaisman²⁸ evaluated 485 patients with reported PCN allergy. Using a conservative (sensitive) approach to identify allergy by history, he implemented a process to go directly to intravenous cefazolin surgical prophylaxis in low-risk patients. This was done in 267 patients (55%) without adverse reactions. Vorobeichik²⁹ recently performed an extensive review of the anesthesia literature. He concluded that overall anaphylaxis rates were extremely low (.0004%), and cited studies which found only 3 cases of cephalosporin anaphylaxis in >65,000 cases where patients had a history of PCN allergy and were administered perioperative cephalosporins. These rates were not significantly higher than patients who report no prior allergy history.

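### In Appendix B, Question 8 has no answer for a course already over when the reaction began, and Question 1's time bands are not contiguous and have no rounding rule

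*Protocol*

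**What the plan says.** Protocol Appendix B, Section 1, Question 8 reads "Did you stop taking the antibiotic or did you finish the course". Three answers follow: "Stopped after the reaction started", "Continued to take the antibiotic after the reaction" and "c. Don't remember". The stem names finishing as a possibility, but no answer records it.

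Question 1 asks "How long ago was the reaction to the antibiotic". The bands are under 6 months, 6 months to 1 year, 2 to 5 years, 6 to 10 years and over 10 years, plus an unknown option. Neither document says how part-years are to be rounded.

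Question 6 splits hives at 5 years and carries that limit in its own wording: the low-risk item is "Hives (greater than 5 years ago"), and the higher-risk item is hives at 5 years or less.

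Protocol section 8.4.1 and SAP section 7.3 build the short form from this questionnaire. They use item response theory to "evaluate each question item's discrimination ability of true PCN (B-lactam) allergy", then variable importance, then a method such as random forest, and choose the 4-6 question set with the highest negative predictive value. SAP section 5 treats missing data as missing at random, without imputation, unless evidence suggests otherwise.

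**The concern.** Stopping and continuing both presuppose that doses remained. A person with none left must give an untrue answer, say that they do not remember, or leave the item blank. The two untrue answers carry opposite meanings: 'stopped' suggests a reaction that ended treatment, and 'continued' suggests that further doses were tolerated. The questionnaire itself foresees such people, since it lists injection (Question 3), onset 24 hours or more after the first dose (Question 4) and one day of treatment (Question 5).

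For reactions other than hives, Question 1 is the only item that records elapsed time. Its two gaps lie next to the one-year and five-year limits used in the risk stratification described in Protocol section 2.1.

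The short form is part of the first primary objective. Noise in a candidate item weakens its observed link with reactivity, so a useful question may be ranked too low. A question that is selected with its answer list unchanged would take the same gap into clinic use.

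**Working it through.** The plan gives no figure on this point, so there is nothing to reproduce. The check has three parts.

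**1. Question 8 against a course already over at onset.** None of the three answers is true of this person (0 of 3). Other items help only in part:

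- Question 5, one day only, fits a single-dose patient. It also fits someone prescribed a longer course who quit after the first day. If the single-dose patient picks 'stopped', the two give identical answers to Questions 5 and 8.
- Question 3, injection, separates some of these.
- Question 7, option h, records that the antibiotic was discontinued, not whether doses were still due.
- A reaction after a completed longer course cannot be recovered, because Question 4's last band is open-ended and cannot be set against the length of the course.

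**2. Question 1 under three readings.**

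| Reading | Years with no band | 1.5 years ago | 5.5 years ago |
|---|---|---|---|
| Exact elapsed time | 2 (between 1 and 2, and between 5 and 6) | none | none |
| Completed whole years | 0 | 6 months to 1 year | 2 to 5 years |
| Nearest whole year | 0 | 2 to 5 years | 6 to 10 years |

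Under completed years, the 2 to 5 band also takes in reactions from just over 5 to just under 6 years ago. Under nearest year it takes in those from just over 5 to just under 5.5 years ago.

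**3. Illustrative dilution for Question 8.** From Protocol section 8.2: 5% higher-risk histories leave 0.95 × 1,000 = 950 tested, and 3% reactive gives 950 × 0.03 = 28.5 reactors. Assumed, not in the documents: among people with doses left, 60% stopped and 40% continued; true odds ratio 0.30 for continued against stopped; 3% reactive among people with no dose left; share *s* with no dose left.

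Risks of 4.15% (stopped) and 1.28% (continued) satisfy the inputs: 0.6 × 4.15% + 0.4 × 1.28% = 3.0%, and (0.0128/0.9872) / (0.0415/0.9585) = 0.30.

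With an even split, the recorded risks are:

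- stopped: [0.6(1−s) × 4.15% + (s/2) × 3%] / [0.6(1−s) + s/2]
- continued: [0.4(1−s) × 1.28% + (s/2) × 3%] / [0.4(1−s) + s/2]

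At s = 30%, stopped is (0.42 × 4.15% + 0.15 × 3%)/0.57 = 3.84% (using the unrounded 4.146%), and continued is (0.28 × 1.28% + 0.15 × 3%)/0.43 = 1.88%. The odds ratio is (0.0188/0.9812) / (0.0384/0.9616) = 0.48.

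If all answer 'stopped', the continued risk stays at 1.28%. At s = 30% the stopped risk is (0.42 × 4.15% + 0.30 × 3%)/0.72 = 3.67%, odds ratio 0.34.

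Power below is for a two-sided Fisher test at 5%, summing the two binomial distributions at the expected group sizes. 'Own category' compares stopped with continued among the 950(1−s) people who had doses left.

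| s | OR, even split | Power, even split | OR, all 'stopped' | Power, all 'stopped' | Power, own category |
|---|---|---|---|---|---|
| 5% | 0.33 | 69% | 0.31 | 69% | 72% |
| 10% | 0.36 | 63% | 0.31 | 67% | 69% |
| 20% | 0.42 | 49% | 0.33 | 58% | 62% |
| 30% | 0.48 | 37% | 0.34 | 47% | 56% |

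**The case against.** The best case for leaving the form alone is this. Study staff administer the questionnaire and can help people answer. Whole-year bands are ordinary, and under either whole-year reading nobody lacks a Question 1 band. Questions 3, 5 and 7 sit in the same pool, so a multivariable model can use them jointly with Question 8. The affected share, the 60:40 split and the odds ratio are all assumed. A Fisher test on one item is not how the plan selects questions, and the SAP's item-by-item test of negative predictive value covers only the low-risk symptom items, not Questions 1 or 8. Nothing fixes the wording of the short form, and neither item may be chosen.

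Most of this stands and limits the size of the point. It does not supply the missing answer or the missing rounding rule.

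A reader might infer more than the documents support, in four ways:

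- *Whole groups are miscoded.* Neither document says how these people are recorded. They could be given a wrong answer, placed under non-recall, or left blank and handled as missing.
- *The Question 1 gap undermines the hives classification.* It does not. Classification uses Question 6, which has its own 5-year wording, and nothing asks Question 1 to confirm it.
- *Protocol section 2.2.4 shows that the Question 8 group is large*, because in the STD setting "antibiotic therapy is either single dose or very short term". That sentence concerns how STDs are treated. Question 8 concerns the past course behind the reported reaction, for any indication and possibly more than 10 years ago.
- *A percentage of people falls in the Question 1 gaps.* Any such figure needs a distribution of reaction dates, which the documents do not give, and answers in exact elapsed time.

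**Conclusion.** The point holds as a minor defect of the instrument. Question 8 has no true answer for a course already complete at onset, and existing items repair this only in part. Question 1 allows the same reaction, if 1 to 2 or 5 to 6 years ago, to fall in different bands depending on who records it. Risk classification, and so who is tested, is unchanged.

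The effect on item selection is unknown, because the affected share is not stated and the plan's own selection procedure was not simulated. Under the assumptions shown, about 5% affected costs roughly 3 points of single-item power. If everyone affected answers 'stopped', the odds ratio barely moves (0.31 to 0.34); the power cost is 2 to 4 points up to 20% affected and about 10 points at 30%. The material case is 30% affected and split evenly: odds ratio 0.48 instead of 0.30, and power of 37% against 56% with a separate category. With about 28 expected reactors there is little room for noise that could be avoided so cheaply.

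**What to change.** Add to Question 8: *No further doses were due (single dose, or course already finished)*, and analyse it as its own category.

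Make Question 1 contiguous: *<6 months; 6 months to 1 year; more than 1 to 5 years; more than 5 to 10 years; more than 10 years*, keeping the unknown option. The 5-year edge then agrees with the limit in the hives items of Question 6.

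The cost is two answer-list edits in the electronic form, with no extra time for subjects. If enrolment has begun, answers collected before and after the change are not interchangeable and need a version flag in the analysis, which is the one small downside. No dose, eligibility criterion or clinical rule changes.
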